4.2 Rationale for the Proposed Study

In Europe and the U.S., the efficacy and safety of Lu AA21004 were demonstrated at doses of 5 to 20 mg/day and Lu AA21004 has already been approved for marketing. For 2 short-term studies (Studies CCT-002 and CCT-003) including Japanese MDD patients, there are no statistically significant differences in the efficacy between any Lu AA21004 groups and the placebo group; however, in Study CCT-002, changes from baseline in the MADRS total score in the 10 and 20 mg groups were greater than in the placebo group in both overall population and Japanese population, and these results appeared to be supported by the result of 10 mg group in Study CCT-003.

Based on these results, if a statistically significant difference between the Lu AA21004 10 or 20 mg group and the placebo group is shown in the planned study (Study CCT-004), it is considered that the hypothesis of the efficacy of Lu AA21004 at doses of 10 and 20 mg in the Japanese population in Study CCT-002 can be verified.

The results of Studies CCT-002, CCT-003 and OCT-001 suggested that there were no significant safety concerns about Lu AA21004 at the dose up to 20 mg, but further data collection may provide more appropriate safety evaluation.

From the above, this study is designed as an additional phase III study to evaluate the efficacy and safety of Lu AA21004 in Japanese patients with MDD.

Pharmacogenomic analyses may be conducted to evaluate a possible contribution of genetic polymorphism on drug response affecting the efficacy and safety of Lu AA21004. Participation of subjects in pharmacogenomic sample collection is optional.

As pharmacogenomics is an evolving science, many genes and their functions are not yet fully understood. Future data may suggest a role of some of these genes in drug response, which may lead to additional hypothesis-generating exploratory research with banked samples.

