4.1.3 Japanese Phase II/III Clinical Studies

In Japan, 2 placebo-controlled, short-term studies (Study CCT-002 [multinational study] and Study CCT-003 [Japan local study]) were conducted in subjects with MDD. In addition, a long-term extension study (Study OCT-001) was conducted in those who completed Study CCT-003.

Study CCT-002 was conducted in 14 countries including Japan, Europe and the Asia Pacific region to evaluate the efficacy and safety of Lu AA21004 at doses of 5, 10 and 20 mg/day. For the mean changes from baseline in the MADRS total score at Week 8 (last observation carried forward [LOCF]) in the primary efficacy analysis (analysis of covariance [ANCOVA]), the mean differences of the Lu AA21004 5, 10 and 20 mg group compared to the placebo group were -0.61 (p = 0.91), -1.69 (p = 0.30) and -1.82 (p = 0.24), respectively. In addition, in the same analysis for Japanese population, the mean differences of the Lu AA21004 5, 10 and 20 mg group compared to the placebo group were 0.89, -2.74 and -3.45, respectively.

In Study CCT-002, Most TEAEs were mild or moderate, and TEAEs reported in more than 5% of subjects in any Lu AA21004 groups were nausea, nasopharyngitis, headache, dizziness, constipation, dry mouth, and insomnia. Of these, TEAEs with higher (≥ 2 -fold) incidence in any Lu AA21004 groups than that in placebo group were nausea, constipation, dry mouth, dizziness and insomnia.

In Study CCT-003, the efficacy and safety of Lu AA21004 at doses of 5 and 10 mg/day were evaluated in Japanese subjects with MDD. For the mean changes from baseline in the MADRS total score at Week 8 (LOCF) in the primary efficacy analysis (ANCOVA), the mean differences of the Lu AA21004 5 and 10 mg group compared to the placebo group were -2.03 (p = 0.10) and -1.04 (p = 0.40), respectively.

In Study CCT-003, TEAEs reported in more than 5% of subjects in any Lu AA21004 groups were nausea, diarrhoea, nasopharyngitis, somnolence, headache, and suicidal ideation. Of these, TEAEs with higher (≥ 2 -fold) incidence in the Lu AA21004 groups than that in the placebo group were nausea and suicidal ideation. For suicidal ideation, the incidence in the 10 mg group (8 subjects; 6.6%) was higher than in the placebo group (2 subjects; 1.6%) and 5 mg group (1 subject; 0.8%). In general, most TEAEs were mild or moderate, suggesting that there were no significant safety concerns about Lu AA21004.

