13.1.3 Efficacy Analysis

Primary Efficacy Analysis for Primary Endpoint

The primary endpoint for this study is the change from baseline (i.e. at the start of double-blind treatment period) in the MADRS total score after 8 weeks of treatment.

Comparisons between each Lu AA21004 treatment group and the placebo group at Week 8 of the double-blind treatment period will be performed using the FAS based on MMRM analysis of covariance with the change from baseline in the MADRS total score as a dependent variable, and visit, treatment group, visit-by-treatment group interaction and baseline MADRS total score-by-visit interaction as fixed effects. An unstructured variance-covariance matrix will be used to model the within-subject errors and Satterthwaite's method will be used to approximate the degrees of freedom. Holm's step down method will be used to adjust the multiplicity for the comparisons. More specifically, let H_{01}, H_{02} be a family of hypotheses as follows:

$$H_{01}: \mu_{\text{Placebo}} = \mu_{10 \text{ mg}}$$

$$H_{02}: \mu_{\text{Placebo}} = \mu_{20 \text{ mg}}$$

Then let P_1 and P_2 denote the unadjusted p-values of tests for H_{01} and H_{02} , respectively. Order the p-values from the smallest to the largest, $P^{(1)}, P^{(2)}$ and let the corresponding null hypotheses be $H^{(1)}, H^{(2)}$. Holm's step-down method proceeds as follows:

Step 1: if $P^{(1)} > 0.025$, retain both null hypotheses $H^{(1)}$ and $H^{(2)}$, and stop. If $P^{(1)} \leq 0.025$, reject null hypothesis $H^{(1)}$ and go to Step 2.

Step 2: if $P^{(2)} > 0.05$, retain null hypothesis $H^{(2)}$. If $P^{(2)} \leq 0.05$, reject null hypothesis $H^{(2)}$.

Secondary Efficacy Analyses for Primary Endpoint

To check the robustness of the results, the same analysis as used for the primary efficacy analysis will be performed using the PPS.

For the FAS, an analysis of covariance (ANCOVA) model with the change from baseline in the MADRS total score after 8 weeks of treatment (values at Week 8 [LOCF] – baseline) as a dependent variable, treatment group as a fixed effect and the baseline MADRS total score as a covariate will be applied for comparisons between the placebo group and each Lu AA21004 treatment group.

Analyses for Secondary Endpoints

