13.3 Determination of Sample Size

A number of subjects planned to be enrolled in this study is 480 (160 per group). Assuming the true mean differences of 3.5 for the change from baseline in the MADRS total score between each Lu AA21004 group and the placebo group, this sample size will provide greater than 80% power to detect the difference between each Lu AA21004 group and the placebo group by 2-sample t-test. In addition, assuming the true mean differences of 3.0 for the change from baseline

in the MADRS total score between each Lu AA21004 group and the placebo group, this sample size will provide greater than 80% power to detect the difference between either the Lu AA21004 10 mg or 20 mg group and the placebo group. These power calculations assume a common standard deviation of 9.5 for the change from baseline in the MADRS total score, with a 2-sided level of 0.025.

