2.1 Primary Endpoint(s) and Analytical Methods

2.1.1 Primary Analysis

Analysis Set: Full Analysis Set

Analysis Variable(s): Change from baseline in the MADRS total score at Week 8 of treatment with double-blind study drug

Analytical Method(s): Primary efficacy analysis will be performed based on a mixed model for repeated measurements (MMRM) analysis of covariance with change from baseline in MADRS total score at each post-dose visit as a dependent variable, and visit, treatment group, visit-by-treatment group interaction, baseline MADRS total score-by-visit interaction as fixed effects.

Comparisons between each Lu AA21004 group and the Placebo group will be performed at Week 8 of treatment with double-blind study drug. For the adjustment of freedom degree, Satterthwaite method will be used. For covariance structure analysis among the subjects, the same, unstructured covariance matrix is assumed.

[Model]

Change from baseline in the MADRS total score = Visit + Treatment group + Treatment group \times Visit + baseline MADRS total score \times Visit

Holm adjustment will be used for multiplicity for the comparison. That is,

$$H_{01}: \mu_{\text{Placebo}} = \mu_{10 \text{ mg}}$$

$$H_{02}: \mu_{\text{Placebo}} = \mu_{20 \text{ mg}}$$

A p-value for each null hypothesis will be set to be P_1 and P_2 . A test will be performed according to the following procedures after setting P_1 and P_2 in an ascending order as $P^{(1)}$ and $P^{(2)}$ and setting the corresponding null hypotheses as $H^{(1)}$ and $H^{(2)}$.

Step 1: In the case of $P^{(1)} > 0.025$, end the test procedures by holding null hypotheses $H^{(1)}$ and $H^{(2)}$. In the case of $P^{(1)} \leq 0.025$, reject null hypothesis $H^{(1)}$ and proceed to Step 2.

Step 2: In the case of $P^{(2)} > 0.05$, hold null hypothesis $H^{(2)}$. In the case of $P^{(2)} \leq 0.05$, reject null hypothesis $H^{(2)}$.

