2.4.5 Multiple Comparison/Multiplicity

The main focuses will be placed on the results of the primary analysis performed for the primary endpoint defined as change from baseline in the MADRS total score at Week 8 in the full analysis set. In the primary analyses, each Lu AA21004 group will be compared with the placebo group based on Holm's method to maintain the overall type I error rate below 5%. Other analytical results will be interpreted to support the results of the primary endpoint or to explore the characteristics of the efficacy of Lu AA21004. These results will be considered one measure suggesting the trends or characteristics of the efficacy. Thus, no adjustments for multiplicity will be performed.

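### Does Protocol 4.2 let a significant result at one dose count as proof of efficacy at both 10 mg and 20 mg?

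*Protocol*

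**What the plan says.** **Rationale.** Protocol 4.2 states a condition, "if a statistically significant difference between the Lu AA21004 10 or 20 mg group and the placebo group is shown in the planned study", and then a conclusion: "the hypothesis of the efficacy of Lu AA21004 at doses of 10 and 20 mg in the Japanese population in Study CCT-002 can be verified". All the protocol editions supplied carry the same wording.

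**Test.** Protocol 13.1.3 sets two null hypotheses, placebo against 10 mg and placebo against 20 mg. The smaller p-value is compared with 0.025. If it passes, the larger is compared with 0.05, and that null is retained if the p-value is above 0.05. SAP 2.1.1 repeats the rule. SAP 2.4.5 has each dose compared with placebo by Holm's method "to maintain the overall type I error rate below 5" per cent.

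**Sample size.** Protocol 13.3 gives two power statements. The first, at a true difference of 3.5, is for each dose. The second, at 3.0, is "greater than 80% power to detect the difference between either the Lu AA21004 10 mg or 20 mg group and the placebo group".

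**The concern.** The sentence in 4.2 starts with two doses joined by *or* and ends with the same doses joined by *and*. If *or* means at least one, a significant result at 20 mg alone would count as verification for 10 mg as well, while 13.1.3 would retain the 10 mg null. The protocol would then say two things about the same dose.

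The at-least-one reading is not far-fetched, because the second power statement in 13.3 aims at exactly that kind of success. A split result is also realistic on the protocol's own figures. At stake would be an efficacy claim for a dose that had failed its own test, outside the error control that Holm's procedure provides.

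**Working it through.** **1. Reproduce the plan's power.** Inputs from Protocol 13.3: 160 per group, SD 9.5, two-sided level 0.025, differences 3.5 and 3.0. Allocation is 1:1:1 (Protocol 6.1), so the two comparisons share the placebo arm and their test statistics have correlation 0.5.

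- Standard error of a difference: 9.5 × √(2/160) = 1.062.
- Critical value at two-sided 0.025: 2.241.
- Each dose at 3.5: 3.5/1.062 = 3.295, and Φ(3.295 − 2.241) = 85.4% (85.1% by the noncentral t).
- One named dose at 3.0: 3.0/1.062 = 2.825, and Φ(2.825 − 2.241) = 72.0%.
- At least one dose at 3.0, bivariate normal with correlation 0.5: 85.8%.

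Both statements of more than 80% power hold.

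**2. What a split result looks like.** Step 1 needs an observed difference of about 2.241 × 1.062 = 2.38 points. Step 2 needs about 1.960 × 1.062 = 2.08. Observed differences of 3.0 and 1.5 would reject one null and retain the other.

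**3. How often it happens.** Normal approximation, Holm at 0.025 then 0.05, no dropout:

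| True difference, 10 / 20 mg | Source | At least one | Both | Exactly one | One-dose share of wins |
|---|---|---|---|---|---|
| 3.5 / 3.5 | Protocol 13.3 | 94.5% | 84.1% | 10.4% | 11% |
| 3.0 / 3.0 | Protocol 13.3 | 85.8% | 68.6% | 17.3% | 20% |
| 2.74 / 3.45 | Protocol 4.1.3, Japanese subjects in CCT-002 | 89.3% | 68.7% | 20.6% | 23% |

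The procedure controls error as intended. With no effect at either dose, it rejects at least one null in 4.6% of trials. With 0 at 10 mg and 3.5 at 20 mg, it rejects the true 10 mg null in 4.4%.

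**4. Set the passages side by side.**

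- Protocol 6.2.3 uses the same sentence frame as 4.2. It lists 5, 10 and 20 mg joined by *or* against placebo, then gives three estimates in order (−2.3, −3.6, −4.6). There *or* can only mean each dose in turn.
- The primary objective in 5.1.1 joins the two fixed doses with *or* when both are plainly under study.
- Where 13.3 means at least one dose, it writes *either* and contrasts it with *each*. Section 4.2 has no *either*.
- Read dose by dose, 4.2 says that significance at a dose verifies the CCT-002 hypothesis for that dose. That agrees with Holm's procedure.

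**5. Which passage governs.** Protocol 13.1 assigns analysis methodology to the SAP. Protocol 13.1.3, SAP 2.1.1 and SAP 2.4.5 agree with one another. None of them refers to 4.2 or lets one dose's result carry over to the other.

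**The case for a change.** The best case for a change is that 4.2 is the only place that says in words what a significant result would establish, and it says so too broadly. SAP 2.4.5 controls the error rate but does not spell out what a one-dose win supports. Nor do the protocol's own data make it safe to infer one dose from another. In CCT-003 the 5 mg difference (−2.03) was larger than the 10 mg difference (−1.04). In the meta-analysis 15 mg (−2.6, not significant) fell below both 10 mg (−3.6) and 20 mg (−4.6). A clarifying sentence would cost nothing.

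Part of this stands. The sentence is loosely written, and a literal reader could take it the wrong way. The rest does not carry. Rejecting or retaining a named null hypothesis already states what is concluded for that dose, so an added sentence would repeat 13.1.3.

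The percentages do not measure harm either. They describe the normal behaviour of a correct procedure and become errors only if 4.2 overrides 13.1.3, which no passage says. The same goes for the extreme case of no effect at 10 mg and 3.5 at 20 mg. There at least one dose wins in 86% of trials, and a literal 4.2 would extend each win to both doses. That case also assumes a zero effect at 10 mg, which no estimate in the protocol shows.

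**Conclusion.** The concern does not hold as a fault in the plan. Section 4.2 contains a loose conjunction in background text. The testing rule is stated the same way in the protocol and the SAP, is correct, and decides each dose on its own p-value. If only one dose wins, the plan retains the other dose's null, and no claim for that dose follows.

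A split result would arise in roughly 10% to 21% of trials over the three scenarios tabulated, so analysts should expect to apply the rule. The plan already tells them how. The effect of the 4.2 wording on tests, thresholds, sample size and outputs is nil.

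This rests on two readings: that 13.1.3 and the SAP govern inference, which their content and Protocol 13.1 support, and that *or* in 4.2 carries the sense it has in 6.2.3. The first is enough by itself. The frequencies assume the planning SD, no dropout and normal tests in place of the mixed model, and the conclusion does not depend on them.

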5.0 STUDY OBJECTIVES AND ENDPOINTS

5.1 Objectives

5.1.1 Primary Objective

- To evaluate the efficacy of 2 fixed doses of Lu AA21004 (10 or 20 mg/day) after 8 weeks of treatment in Japanese patients with MDD.

5.1.2 Secondary Objectives

- To evaluate the safety and tolerability of 2 fixed doses of Lu AA21004 (10 or 20 mg/day) after 8 weeks of treatment in Japanese patients with MDD.
- To evaluate the efficacy of Lu AA21004 (10 or 20 mg/day) on cognitive functions after 8 weeks of treatment in Japanese patients with MDD.

5.1.3 Additional Objectives

- To analyze the plasma concentrations of Lu AA21004 and its metabolites Lu AA34443 and Lu AA39835 using population pharmacokinetic analyses.

5.2 Endpoints

5.2.1 Efficacy Endpoints

5.2.1.1 Primary Endpoint

- Change from baseline (i.e. at the start of the double-blind treatment period) in the MADRS total score after 8 weeks of treatment.

5.2.1.2 Secondary Endpoints

- MADRS response after 8 weeks of treatment (LOCF).
(MADRS response is defined as a $\geq 50\%$ decrease in the MADRS total score from baseline).
- MADRS remission after 8 weeks of treatment (LOCF).
(MADRS remission is defined as the MADRS total score of ≤ 10).
- Change from baseline in the Hamilton Depression Rating Scale (HAM-D17) total score after 8 weeks of treatment (LOCF).
- Clinical global impression scale-Improvement (CGI-I) score after 8 weeks of treatment (LOCF).
- Change from baseline in the clinical global impression scale-Severity (CGI-S) score after 8 weeks of treatment (LOCF).
- Change from baseline in the Sheehan Disability Scale (SDS) score after 8 weeks of treatment (LOCF).

- Change from baseline in the Digit Symbol Substitution Test (DSST) score after 8 weeks of treatment (LOCF).
- Change from baseline in the Perceived Deficits Questionnaire (PDQ-5) score after 8 weeks of treatment (LOCF).

5.2.2 Pharmacokinetic Endpoint

- Plasma concentrations of Lu AA21004 and its metabolites Lu AA34443 and Lu AA39835.

5.2.3 Safety Endpoints

- Adverse events
- Weight
- Vital signs
- Electrocardiograms (ECGs)
- Clinical laboratory tests (serum chemistry, hematology and urinalysis)
- Columbia-Suicide Severity Rating Scale (C-SSRS)

6.0 STUDY DESIGN AND DESCRIPTION

6.1 Study Design

[figure not shown]
This is a randomized, double-blind, placebo-controlled, parallel-group, phase III study to evaluate the efficacy and safety of 8-week treatment of 2 fixed doses of Lu AA21004 (10 or 20 mg/day) in Japanese subjects with MDD.

This study consists of a 1-to 3-week screening period, a 1-week single-blind placebo lead-in period, an 8-week double-blind treatment period and a 4-week safety follow-up period. Subjects who fulfill all inclusion criteria and none of exclusion criteria at the start of screening period (Visit 1) and at the start of placebo lead-in period (Visit 2) will move into the placebo lead-in period and receive placebo once daily for 1 week in a single-blind manner. Afterwards, those who fulfill all the inclusion criteria and none of the exclusion criteria at the start of double-blind treatment period (Visit 3) will move into the double-blind treatment period and will be randomized in a 1:1:1 ratio to one of the following treatment groups: the placebo group, the Lu AA21004 10 mg/day group or the Lu AA21004 20 mg/day group. Subjects in the placebo group and the Lu AA21004 10 mg/day group will receive placebo and Lu AA21004 10 mg, respectively, once daily from the day after Visit 3 for 8 weeks in a double-blind manner. Subjects in the Lu AA21004 20 mg/day group will receive Lu AA21004 10 mg once daily from the day after Visit 3 for 1 week and thereafter Lu AA21004 20 mg once daily for 7 weeks in a double-blind manner. Subjects in any treatment groups will visit study sites at Week 1, 2, 4, 6 and 8 during the double-blind treatment period for examinations/observations/assessments.

A safety follow-up contact (visit or phone call) will be made 4 weeks after the completion of the double-blind treatment period. Subjects who prematurely discontinue the study during the placebo lead-in period or the double-blind treatment period will be requested to visit the study site for the end-of study assessments within 7 days after the discontinuation decision is made wherever possible, and will be contacted 4 weeks after the last dose of the study medication for safety follow-up.

A schematic of the study design is shown in [Figure 6.a](#).

A schedule of examinations/observations/assessments is listed in [Appendix A](#).

W: week, V: visit, QD: once daily

- a) Subjects will be randomized on the day of visit at the start of double-blind treatment period (Day -1). Subjects will start the double-blind treatment from the next day (Day 1).
- b) Subjects will receive 10 mg/day for the first 1 week, and then increase the dose to 20 mg/day from the 2nd week.
- c) Safety follow-up assessment will be conducted by visit to the site or on telephone.

Figure 6.a Schematic of Study Design

6.2 Justification for Study Design, Dose, and Endpoints

6.2.1 Subject Population

It has been reported that the placebo response rate in subjects with single major depressive episode is higher than that in subjects with recurrent major depressive episode.[\[5\]](#) Since it is important to exclude subjects with high placebo response from clinical studies of antidepressants, subjects with recurrent major depressive episode are eligible for this study. In order to adequately evaluate the efficacy and safety, subjects with moderate to severe MDD are eligible for this study, and subjects with mental disorder other than MDD are excluded from this study.

6.2.2 Study Design

This study is designed based on Guideline for Clinical Evaluation of Antidepressants (Notification No. 1116-1 of PFSB/ELD dated 16 November 2010).^[3]

A double-blind, randomized, placebo-controlled study is designed for adequate evaluation of the drug efficacy and safety and is used as a standard study design for antidepressants. The use of placebo has continued to be a subject of discussion on the grounds of possible worsening of depressive symptoms or potential increase in suicidal risk; however, there is no evidence that assignment to placebo results in permanent harm or an increased risk of committing suicide. Subjects at significant risk of suicide are ineligible for this study. Furthermore, suicidal risk of a subject will be assessed using C-SSRS at every visit.

The subjects will be informed about the possibility of receiving placebo, the possible risks with placebo, and their right to withdraw from the study at any time. To a subject who discontinues the study, any other appropriate treatment will be provided based on the investigator's decision.

In addition, a 1-week placebo lead-in period is set prior to the double-blind treatment period to exclude subjects who highly respond to placebo from the study, and thereby subjects who have significantly improvement or aggravation of depressive symptoms during the placebo lead-in period will be excluded.

Justification for sample size is described in Section 13.3.

6.2.3 Doses

In overseas phases II and III studies, the efficacy of Lu AA21004 at doses of 5, 10 and 20 mg/day was shown, with no significant safety concerns. In addition, based on the results of meta-analyses in 11 placebo-controlled, double-blind, short-term studies, the differences of the mean changes from baseline in the MADRS total score at Week 6 or 8 between the Lu AA21004 5, 10 or 20 mg group and the placebo group were -2.3 (p =0.007), -3.6 (p <0.001), and -4.6 (p <0.001), respectively, showing that the difference with the placebo group became greater with the dose increase of Lu AA21004.

In Study CCT-002 for subjects with MDD including Japanese, Lu AA21004 was safe up to a dose of 20 mg/day. And although no statistically significant differences had been demonstrated in the efficacy between the Lu AA21004 groups and the placebo group, the efficacy of Lu AA21004 in the 10 and 20 mg groups was greater than in the placebo group in both overall population and Japanese population.

From the results of previous Japanese and overseas studies above, since there were no significant safety concerns about Lu AA21004 up to a dose of 20 mg/day and Lu AA21004 at doses of 10 and 20 mg/day is expected to be effective, these 2 doses will be assessed in this study.

